### 11.3.5 Specular Microscopy

**Endothelial Cell Density:** Endothelial cell density average (cells/mm^2) will be assessed using specular microscopy performed on the central cornea of each eye at Screening, Week 4, Week 12, Week 24, Week 40, and Week 52/Exit.

Endothelial cell density at baseline (Screening) and raw values and their changes from baseline will be summarized descriptively by visit for each eye.

In addition, the number and percentage of patient-eyes that showed following

- beyond 200 cells/mm^2 increase
- within 200 cells/mm^2 increase
- within 200 cells/mm^2 decrease
- ≥ 10% loss
- ≥ 20% loss
- ≥ 30% loss
- ≥ 40% loss
- ≥ 50% loss
- ≥ 10% and < 20% loss
- ≥ 20% and < 30% loss
- ≥ 30% and < 40% loss
- ≥ 40% and < 50% loss

in endothelial cell density change from baseline will be summarized by visit for each eye. Percent change from baseline is defined as:  $100 \times (\text{At Visit ECD} - \text{Baseline ECD}) / (\text{Baseline ECD})$  where ECD = endothelial cell density. For the ECD decrease, the worst ECD assessment within the given analysis visit window (or analysis cycle) including unscheduled visits will be summarized by visit and by analysis cycle. For the ECD increase, the maximum ECD assessment will be summarized by visit and by

analysis cycle. Listings for patients with 20% or more central corneal endothelia cell density (CECD) loss at any visit will be provided.

**Coefficient of Variation Average (CVAVE):** Coefficient of variation average of raw data and changes from baseline will be summarized descriptively by visit for each eye.

**Pleomorphism Average (HEXAVE):** Pleomorphism average of raw data and their changes from baseline will be summarized descriptively by visit for each eye.

### 11.3.6 Pachymetry

Corneal thickness using ultrasound (contact) pachymetry is performed on the central cornea for each eye at Screening, Week 4, Week 12, Week 24, and Week 52/Exit visits. At each examination, 3 measurements of central corneal thickness (CCT) and associated standard deviation is reported, and the average of the 3 measurements will be calculated and used for analysis. CCT raw values and their changes from baseline at each post-Baseline visit will be summarized descriptively by visit for each eye.

### 11.3.7 Biomicroscopy and Dilated Ophthalmoscopy

Biomicroscopy will be performed in each eye by slit-lamp examination at Screening, Baseline, and during Cycle 1, Cycle 2, Follow-up, and during Cycle 3 for Stage 1 patients.

At these exams, any findings noted on the following will be recorded for each eye on the eCRF as follows:

- Eyelids/Eyelid Margins/Lashes
  - Erythema
  - Edema
  - Other
- Conjunctiva (Bulbar or Palpebral)
  - Hyperemia
  - Edema
  - Subconjunctival Hemorrhage
  - Pterygium, encroaching on visual axis
  - Pterygium, not encroaching on visual axis
  - Other
- Cornea
  - Punctate Epithelial Staining
  - Infiltrates
  - Edema
  - Corneal Guttata
  - Endothelial Pigment

- Keratic Precipitates
- Neovascularization
- Opacity(ies)
- Stromal Haze
- Other
- Anterior Chamber
  - Cells
  - Flare
  - Hypopyon
  - Hyphema
  - Other
- Iris/Pupil
  - Afferent Pupillary Defect (APD)
  - Posterior Synechiae
  - Transillumination Defect(s)
  - Pseudoexfoliative Material
  - Peripheral Iridectomy
  - Laser Peripheral Iridotomy
  - Other

Severity of findings in the categories of Eyelids/Eyelid Margins/Lashes, Conjunctiva (Bulbar or Palpebral) and Cornea will be recorded as +0.5 (Trace), +1 (Mild), +2 (Moderate), +3 (Severe) or Not Applicable. Severity of Anterior Chamber findings will be recorded as +0.5, +1, +2, +3, +4, or Not Applicable using the Standardization of the Uveitis Nomenclature (SUN) Working Group criteria. No severity grade will be assigned for Iris/Pupil findings, and only findings noted will be recorded.

Biomicroscopy findings will be coded using MedDRA. Number and percentage of patient eyes with findings showing more than one grade increase from baseline will be presented by coded PT (more than 1 severity grade increase means a change from 0 to 2 and above, from 0.5 to 2 and above, or from 1 to 3 and above from baseline at any of the follow-up visits). Number and percentage of patient eyes with findings present at post-baseline which did not present at baseline will be summarized (i.e., findings not associated with a severity grade). The analysis results will be presented by study periods and analysis cycle.

Dilated ophthalmoscopy and lens status and opacity assessments will be performed in each eye at Screening, Baseline, Week 12, Week 24, Week 40, and Week 52/Exit. At ophthalmoscopy exams, any findings noted on the following areas will be recorded for each eye:

- Vitreous (each finding will be entered as free text field)
- Macula (Intraretinal Fluid or Other (other is entered as free-text))

- Retina Periphery (each finding will be entered as free text)
- Optic Nerve Exam – Cup/Disc Ratio Disc examination findings will be recorded under 2 sub-categories; Disk Hemorrhage, and Other Disc Pathology (other pathology is entered as a free text)

Dilated ophthalmoscopy findings will be coded using MedDRA. Similar analysis from Biomicroscopy will be performed for ophthalmoscopy findings.

Optic Nerve cup/disc ratio is evaluated using a 0.0 to 1.0 scale, with larger values indicating glaucoma or other pathologies, thus a reduction from baseline is considered an improvement. Categorical changes in cup/disc ratio from baseline will be summarized by each post-Baseline assessment visit. Change from baseline at each follow-up visit (visit value – baseline values) will be categorized as an improvement of 0.2 or more ( $\leq -0.2$ ), no change - between 0.2 and -0.2 ( $> -0.2$  to  $< 0.2$ ), or a worsening if the ratio increases by 0.2 or more (i.e., change  $\geq 0.2$ ). The number and percentage of patients in each category will be provided for each eye by assessment visit.

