efficacy analysis, and allows for assessment of the duration of effect of 2 Bimatoprost SR administration cycles throughout the study. With the implementation of Amendment 3, Allergan is discontinuing the administration of the Bimatoprost SR 15 µg dose strength to patients based on a thorough review of the long-term Bimatoprost SR safety data from the recently completed and ongoing studies. The discontinuation is based on the conclusion that corneal adverse events associated with repeat administrations of the 15 µg dose strength are no longer supported by a favorable benefit:risk consideration.

The comparator that is to be administered in the contralateral eye is selective laser trabeculoplasty (SLT), which is also indicated for this patient population. SLT, one of the most frequently used LT modalities, is commonly used as an intermediate step between topical medications and incisional glaucoma surgery and is comparable in efficacy and durability to argon laser trabeculoplasty (ALT) (Damji et al, 1999; Damji et al, 2006; Martinez-de-la-casa et al, 2004; Rolim de Moura et al, 2007; Wang et al, 2013). SLT causes minimal tissue destruction compared with ALT and is increasingly being adopted as the LT standard of care (Realini, 2008). SLT has been reported to reduce IOP effectively in eyes with OHT and OAG, as reports often suggest IOP reduction to be similar to topical prostaglandin analogues (Katz et al, 2012; Nagar et al, 2009; McAlinden 2014). This study is 1 of 2 phase 3 studies that will compare the IOP-lowering effects and safety profiles of Bimatoprost SR and SLT.

2. Study Objectives and Clinical Hypotheses

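### New trace or mild corneal and anterior chamber findings, and mild-to-moderate worsening, are listed but enter no slit-lamp summary table

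*SAP*

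**What the plan says.** SAP 11.3.7 plans two biomicroscopy summaries, both by study period and analysis cycle.

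- Graded findings: "Number and percentage of patient eyes with findings showing more than one grade increase from baseline will be presented by coded PT". The definition is "more than 1 severity grade increase means a change from 0 to 2 and above, from 0.5 to 2 and above", and then 1 to 3 or higher, at any follow-up visit.
- New findings: "findings present at post-baseline which did not present at baseline will be summarized (i.e., findings not associated with a severity grade").

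The same section fixes which categories have grades. For the cornea (edema, keratic precipitates, stromal haze, guttata and others): "Cornea will be recorded as +0.5 (Trace), +1 (Mild), +2 (Moderate), +3 (Severe) or Not Applicable". For the anterior chamber (cells, flare and others): "Severity of Anterior Chamber findings will be recorded as +0.5, +1, +2, +3, +4, or Not Applicable". Only one category is ungraded as a whole: "No severity grade will be assigned for Iris/Pupil findings, and only findings noted will be recorded".

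Protocol 1.3 explains why dosing was stopped: "corneal adverse events associated with repeat administrations of the 15" µg strength were judged to have made the benefit-risk balance unfavorable.

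**The concern.** The two summaries do not meet. The first has a floor of more than one grade, and the second leaves out anything that has a grade. A cornea going from clear to mild edema, or an anterior chamber going from clear to +1 cells, falls between them at every visit. So does an eye that enters with a mild corneal finding and becomes moderate. That last case is possible under the entry rules, because Protocol 4.4 (exclusion 14) admits stable mild guttata.

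At stake is how completely the report describes the tissue behind the dose discontinuation. Comparing Bim SR and SLT eyes on low-grade slit-lamp findings would mean counting by hand from listings, or relying on whatever was also reported as an adverse event.

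**Working it through.** **Inputs.** All come from SAP 11.3.7. The corneal scale is 0, 0.5, 1, 2, 3. The anterior chamber scale is 0, 0.5, 1, 2, 3, 4. Zero does not appear among the recorded grades; I take it to mean that no finding was noted, as the SAP's own definition does. The counted rises are 0 to 2 or higher, 0.5 to 2 or higher, and 1 to 3 or higher.

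**Number of possible rises.** With k levels there are k(k − 1)/2 upward changes. Cornea: 5 × 4 / 2 = 10. Anterior chamber: 6 × 5 / 2 = 15.

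**Applying the listed definition.**

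| Scale | Counted | Not counted |
|---|---|---|
| Cornea | 5 of 10: 0→2, 0→3, 0.5→2, 0.5→3, 1→3 | 5 of 10: 0→0.5, 0→1, 0.5→1, 1→2, 2→3 |
| Anterior chamber | 8 of 15: 0→2, 0→3, 0→4, 0.5→2, 0.5→3, 0.5→4, 1→3, 1→4 | 7 of 15: 0→0.5, 0→1, 0.5→1, 1→2, 2→3, 2→4, 3→4 |

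**New onset only (baseline 0).** Cornea: 2 of 4 grades counted, with 0.5 and 1 missed. Anterior chamber: 3 of 5 counted, with 0.5 and 1 missed.

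**Does the listed definition match its own label?** On the corneal scale, yes: the five counted changes are exactly those with a difference above 1. On the anterior chamber scale, no: 2→4 differs by 2 but is not listed. Read by its label, the rule would count 9 of 15.

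**Does the second summary catch the remainder?** No. It covers findings without a grade, and every change in the table starts or ends at a recorded grade. A corneal or anterior chamber finding marked Not Applicable for severity could enter it; one graded trace or mild could not.

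**Comparison within the SAP.** SAP 11.3.4 (macroscopic conjunctival hyperemia) applies the same more-than-one-grade cut-off, but beside a summary of the worst severity by eye and period. Trace and mild hyperemia are therefore tabulated. The cornea and anterior chamber have the cut-off row only.

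**The case against.** The strongest reply is that this is a deliberate cut-off for descriptive tables and that the cornea is well covered elsewhere. Much of that stands.

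- **Nothing is hidden.** SAP 16.4 puts all assessments in the data listings and uses all post-baseline assessments for safety evaluation. A reader might infer that adverse event reporting is the only way low-grade findings can be seen. That is wrong: it is the only planned route to a summary by eye, not to visibility.
- **Other corneal tables exist.** The SAP tabulates endothelial cell loss in bands from 10% to 50% (11.3.5), corneal thickness (11.3.6), implant contact with the endothelium (11.3.9), and corneal and anterior segment inflammation events of interest (11.1). The adverse event definition in Protocol 9.1.1 has no severity floor, so mild signs can be reported. These measures do not count slit-lamp grades, however, and the protocol states no rule tying a slit-lamp grade change to an adverse event report.
- **The clinical link is not documented.** A reader might take trace edema or +1 cells as early signs of the harm that ended dosing. Protocol 1.3 refers only to corneal adverse events with repeat administration and does not connect them to low-grade slit-lamp findings.
- **Masking is not repaired.** Protocol 9.4 says the primary investigator is unmasked, which may suggest that slit-lamp counts would be a cleaner source than adverse events. Masked examiners are specified for efficacy IOP readings (Protocol 5.3, 6.1.1, 8.4); no masked slit-lamp grader is required, so extra rows would not remove assessment bias.
- **Table specifications are separate.** SAP 4.0 places them in another document, which may already contain such rows. The SAP text does not plan them.

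The cut-off is legitimate as one row. The reply does not explain why hyperemia gets a full worst-grade summary while the cornea does not.

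**Conclusion.** The gap is real and limited to tabulation. New trace or mild corneal and anterior chamber findings, and a worsening from 1 to 2, are in no biomicroscopy table. By grade steps, half of the possible corneal rises (5 of 10) and 7 of 15 anterior chamber rises are uncounted. These are counts of steps on a scale, not of eyes; the documents give no frequencies from which to estimate eyes affected.

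The missing 2→4 step is a slip in the definition. It probably matters little in practice, since an eye would have to enter with +2 anterior chamber findings and Protocol 4.4 (exclusion 15) screens against active uveitis.

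The conclusion assumes that the restriction to ungraded findings in the second summary is meant literally, and that the separate table specifications do not already add rows. It does not support saying that the corneal signal goes unexamined. This is a cheap improvement to descriptive safety reporting.

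**What to change.** In SAP 11.3.7, for the Cornea and Anterior Chamber categories:

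1. Add, by treated eye and analysis cycle, a shift table from baseline grade to worst post-baseline grade. Alternatively, add two counts: eyes with any new graded finding (0 to 0.5 or more) and eyes with any increase from baseline. The new-finding count would cover 4 of 4 corneal and 5 of 5 anterior chamber onset grades; the any-increase count would cover all 10 and all 15 rises.
2. Keep the more-than-one-grade row, and add 2 to 4 to its anterior chamber definition.
3. Show exams within two days of SLT, sham SLT, implant or sham implant separately from later exams. SAP 11.1 already splits ocular events at two days, but only from the implant or its sham. Protocol 8.4.3.1 also schedules slit-lamp biomicroscopy after the laser on Day 1, and Analysis Cycle 1 starts at SLT (SAP 11.0). Without SLT and sham SLT in the split, that exam would have no stated place.

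Cost: programming a few extra rows from data already collected, with no new visit, procedure or test. Downside: more low-grade, expected post-procedure findings will be tabulated, which the two-day split keeps apart from later ones.

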### **11.3.8 Lens Status and Opacification**

Lens status and lens opacity assessments are performed through a dilated pupil in each eye at Screening, Baseline, Week 12, Week 24, Week 40, and Week 52/Exit. Lens status is assessed as phakic, pseudophakic, or aphakic and recorded on the eCRF.

Lens opacity is assessed by the Age-Related Eye Disease Study (AREDS) as:

- Nuclear cataract
- Cortical cataract
- Posterior subcapsular cataract
- Posterior capsular opacification with location central or peripheral
- Capsular bag not intact, due to central laser/surgical capsulotomy
- Capsular bag not intact, due to capsular tear with location central or peripheral
- Other

At post-Baseline visits, for eyes evaluated as phakic at Baseline, the severity of nuclear, cortical, and posterior subcapsular cataract lens opacities will be summarized ( $<$  standard photo #2, and  $\geq$  standard photo #2) in number and percentage format by visit and eye.

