13. Any history of corneal graft, including partial grafts (eg, Descemet's Stripping Endothelial Keratoplasty [DSEK], Descemet's Membrane Endothelial Keratoplasty [DMEK]); or incisional refractive surgery (eg, radial keratotomy), other than astigmatic keratotomy or limbal relaxing incisions
14. Corneal or other ocular abnormalities that would preclude accurate readings with an applanation tonometer, anterior segment-optical coherence tomography, specular microscope, and/or a contact pachymeter, or could confound study results, eg, moderate to severe corneal dystrophy, including Anterior Basement Membrane Disease (ABMD; ie, Map-Dot-Fingerprint [MDF]) and guttata. Mild ABMD or mild guttata are not exclusionary by clinical examination if, in the opinion of the investigator, the condition is stable and not likely to cause corneal changes during the course of the study.
15. Active or recurrent ocular disease (eg, uveitis, ocular infection, chronic moderate to severe blepharitis or severe dry eye, severe ocular seasonal allergies) or sight threatening diseases (eg, neovascular age-related macular degeneration [ARMD], diabetic macular edema) that, in the opinion of the investigator, would put the patient at a significant risk or would interfere with the interpretation of the study data. Patients with slowly progressive eye diseases (ie, mild cataracts, nonneovascular ARMD) can be enrolled at the discretion of the investigator.
16. Any history of external ocular or intraocular malignancy, and/or any history of benign ocular neoplasia that in the investigator's opinion resulted in clinically significant ocular morbidity

17. History of herpetic ocular diseases (including herpes simplex virus and varicella zoster virus)
18. The following ocular surface findings:
 - a. Bulbar conjunctival hyperemia, on either macroscopic or slit-lamp examination, $> +1$ (mild) at baseline
 - b. Active ocular surface findings other than bulbar conjunctival hyperemia, on either macroscopic or slit-lamp examination, $> +1$ (mild) at Baseline
19. History of moderate or worse ($\geq +2$) bulbar conjunctival hyperemia due to marketed prostaglandin, prostamide, or prostaglandin analog use
20. The anticipated wearing of contact lenses during the study that deviates from the following (contact lens wear is allowed during the study, but is to be temporarily discontinued before study visits, and before and after an Administration Day according to the following):

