treatment regimen assigned at randomization. Patients who have received nonstudy IOP-lowering treatment in both eyes will not receive Bimatoprost SR administration or Sham Bimatoprost SR administration in either eye, and therefore do not need to attend the Bimatoprost SR (or Sham Bimatoprost SR) administration visits and immediate postadministration visits (ie, Bimatoprost SR Cycle 2 administration [Week 16], Cycle 2 Day 2 safety visit, and Cycle 2 Day 4 and Week 2 phone calls, and for Stage 1 patients only, Bimatoprost SR Cycle 3 administration [Week 32], Cycle 3 Day 2 safety visit, and Cycle 3 Day 4 and Week 2 phone calls).

Contact Lenses

Use of soft contact lenses within 3 days and use of rigid gas permeable or hard contact lenses within 1 week prior to a scheduled study visit or Administration Day, or use of contact lenses of any kind within 1 week following any Bimatoprost SR (or Sham) administration in either eye is prohibited.

Other Medications

The following medications (or classes of medications) and treatment procedures are not permitted as concurrent therapy during the study unless the patient has already received nonstudy IOP-lowering medication or treatment in both eyes:

- Subconjunctival, sub-Tenon's, intravitreal, or other ophthalmic injections of any medications in either eye
- Use of any topical ophthalmic medications (except as described above and in [Section 4.5.1](#)) in either eye
- Surgical (incisional and laser) procedures that are not related to study-specific Bimatoprost SR (or Sham) and SLT administration procedures in either eye; patients may exit the study early if an ophthalmic incisional procedure is required
- Oral, intramuscular, or intravenous corticosteroids from 2 months prior to the Baseline visit through study exit
- Use of bimatoprost for hypotrichosis during the study period in either eye
- Use of cyclosporine ophthalmic solution during the study period in either eye
- Systemic use of carbonic anhydrase inhibitor

- Any initiation of or alterations in systemic regimen of beta-blocker containing medications from 2 months prior to screening through the study exit
- Use of corticosteroids in either eye (except as described in [Section 4.5.1](#) for postoperative use) or systemically during the study or historical use prior to Baseline within:
 - 3 years: intraocular fluocinolone acetonide

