## **8.2 BASELINE CHARACTERISTICS**

Baseline characteristics for each eye will be descriptively summarized by treatment of the eye for the following categories: iris color, diagnosis of either OAG (primary OAG, pseudoexfoliation glaucoma, pigmentary glaucoma) or OHT, baseline Hour 0 IOP ( $\leq 25$  mm Hg or  $> 25$  mmHg), iridocorneal angle Shaffer grade, and central endothelial cell density, will be summarized descriptively by treatment group for the ITT population. Study eye iris color will be summarized by color for each of the following categories: monochromic, heterochromic peripupillary, and heterochromic diffuse.

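### The planned lens-opacity summary gives post-treatment prevalence with no baseline comparison, so new opacity cannot be told from old, and it does not say how eyes that lose their natural lens are counted

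*SAP*

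**What the plan says.** Lens status and opacity are "performed through a dilated pupil in each eye at Screening, Baseline, Week 12, Week 24, Week 40, and Week 52/Exit", so a grade exists before treatment and at up to four later visits. The one analysis described for these grades is in SAP 11.3.8: "At post-Baseline visits, for eyes evaluated as phakic at Baseline, the severity of nuclear, cortical, and posterior subcapsular cataract lens opacities will be summarized". Severity is split into two classes at standard photo #2 and shown "in number and percentage format by visit and eye".

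On lens status the same section says: "Lens status is assessed as phakic, pseudophakic, or aphakic and recorded on the eCRF". It plans no summary of changes in that status.

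The baseline list in SAP 8.2 ends with "iridocorneal angle Shaffer grade, and central endothelial cell density, will be summarized descriptively by treatment group for the ITT population"; lens opacity is not in that list. On entry, Protocol 4.4 (criterion 15) states: "Patients with slowly progressive eye diseases (ie, mild cataracts, nonneovascular ARMD) can be enrolled at the discretion of the investigator". On surgery during the study, Protocol 4.5.2 says that "patients may exit the study early if an ophthalmic incisional procedure is required".

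**The concern.** A safety reader wants to know whether lenses in implanted eyes worsen more than lenses in laser-treated eyes. A count of eyes at or above photo #2 at a visit mixes two groups: eyes that were there before treatment and eyes that crossed afterwards. Without the baseline grade beside it, the table cannot separate them. A lens that worsens but stays on the same side of photo #2 does not register at all.

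The section is also silent on eyes that lose phakic status after Baseline. A natural lens that has been removed cannot be graded for nuclear, cortical or posterior subcapsular opacity. Such an eye could be left out of later visits, carried at its last grade or counted as progression, and the text does not choose.

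The SAP handles the neighbouring ocular measures differently. Visual acuity (11.3.2), hyperemia (11.3.4), endothelial cell density (11.3.5), corneal thickness (11.3.6), and biomicroscopy and cup/disc ratio (11.3.7) are all analysed against baseline. Biomicroscopy does not fill the gap: Protocol 6.2 includes the lens in that examination, but the list of findings in SAP 11.3.7 ends at iris and pupil.

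**Working it through.** The plan states no cataract rate, baseline opacity prevalence or surgery rate, so there is no figure to reproduce. What follows is an illustration on assumed inputs.

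**Inputs (all assumed)**
- p0: share of phakic eyes already at or above photo #2 at Baseline, the same for both treatments because the treatment of the primary eye is randomised and the fellow eye receives the other one. Range 0% to 50%.
- i: share of eyes below photo #2 at Baseline that have crossed it by a late visit: 8% for Bim SR, 3% for SLT.
- Eyes at or above photo #2 at Baseline stay there, and no lens is removed.

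**Formulas**
- Progression among eyes at risk: difference = 8% − 3% = 5.0 points; ratio = 8/3 = 2.67.
- Planned table: prevalence = p0 + (1 − p0) × i.
- Displayed difference = (1 − p0) × 5.0 points.

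**Results**

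| p0 | SLT | Bim SR | Difference | Ratio |
|---|---|---|---|---|
| 0% | 3.0% | 8.0% | 5.0 points | 2.67 |
| 10% | 0.10 + 0.90 × 0.03 = 12.7% | 0.10 + 0.90 × 0.08 = 17.2% | 4.5 points | 1.35 |
| 20% | 0.20 + 0.80 × 0.03 = 22.4% | 0.20 + 0.80 × 0.08 = 26.4% | 4.0 points | 1.18 |
| 30% | 0.30 + 0.70 × 0.03 = 32.1% | 0.30 + 0.70 × 0.08 = 35.6% | 3.5 points | 1.11 |
| 50% | 0.50 + 0.50 × 0.03 = 51.5% | 0.50 + 0.50 × 0.08 = 54.0% | 2.5 points | 1.05 |

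Under this model the table keeps a share 1 − p0 of the absolute difference, whatever progression rates are assumed. The ratio falls much faster, because pre-existing opacity is added to both sides.

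**If removed lenses were dropped.** Suppose, purely to show why a rule is needed, that half of the newly crossed eyes are operated on and left out of numerator and denominator. Prevalence becomes [p0 + (1 − p0) × i × 0.5] / [1 − (1 − p0) × i × 0.5]. At p0 = 10% this gives 0.1135/0.9865 = 11.5% for SLT and 0.136/0.964 = 14.1% for Bim SR: 2.6 points, ratio 1.23. At p0 = 30% it gives 2.4 points (1.08), and at p0 = 50%, 1.9 points (1.04). The SAP contains no such dropping rule.

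**The case against.** A reader might infer that the table loses eyes whose cataract is removed, so that the clearest progression disappears. The documents do not support that. SAP 11.3.8 selects eyes by lens status at Baseline and states no rule for dropping them later. Protocol 4.5.2 permits early exit but does not require it. Protocol 8.9 asks for all Week 52/Exit procedures at the last visit of a patient who stops early; these include the dilated examination (8.4.3.14), and lens grading is collected on dilated days (6.2). SAP 16.4 keeps all post-baseline safety assessments in the evaluation and the listings. Anticipated incisional or laser surgery is an entry exclusion (Protocol 4.4, criterion 22), so extraction should be uncommon. What stands is the silence, not a loss of eyes.

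A reader might also infer that a cataract effect of the implant would be hidden. That goes too far for three reasons.
- Ocular treatment-emergent adverse events are tabulated per eye, overall and by period, and the definition covers worsening of events that began before treatment (SAP 11.1). Visual acuity loss of two lines or more is also summarised per eye (11.3.2).
- With randomised paired eyes, the difference in prevalence still carries most of the excess when p0 is modest.
- No document says that a mild cataract reaches photo #2, and entry requires corrected acuity of 20/50 or better in each eye (Protocol 4.3, criterion 15). If few eyes are above the threshold at Baseline, the planned table is close to an incidence table.

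Finally, table layouts are in a separate document (SAP 4.0), so a baseline column may appear there.

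These points limit the size of the concern but do not remove it. Adverse event reporting depends on the investigator, who is unmasked (Protocol 9.4), and the documents state no lens-grade threshold for it. It does not replace an analysis of the grades.

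**Conclusion.** The point holds as a minor gap in the safety analysis. As written, SAP 11.3.8 describes only post-baseline prevalence by visit, so no planned analysis of the collected lens grades shows progression, and eyes that lose phakic status have no stated rule.

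The size depends mainly on a figure the documents do not give. On assumed progression of 8% versus 3%, dilution runs from almost none when baseline prevalence is near zero to half of the absolute difference at 50%. The fall in the ratio is larger but should not be quoted alone. The illustration assumes equal baseline prevalence in the two treatments and no regression below the threshold. The primary efficacy analysis is not affected.

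**What to change.** In SAP 11.3.8:
- Show the Baseline column in the by-visit table and keep that table as supportive.
- For each opacity type, add a shift table from Baseline to the worst post-baseline grade in all eyes phakic at Baseline. If the eCRF holds grades finer than the two classes, which the documents do not say, use them, so that worsening in eyes already above the threshold is visible.
- Report the number and percentage of eyes below photo #2 at Baseline that reach photo #2 or above, by visit and at any time.
- Count a change from phakic to pseudophakic or aphakic through cataract extraction as a progression event. Show these events as a separate component too, because an extraction may have other reasons.

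The cost is one additional table and a short derivation rule. Grades and lens status are already collected, so no visit or procedure changes.
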